5.4. Data Management

5.5. Premature Withdrawal and Missing Data

All subjects who withdraw prematurely from the study/study drug will be documented and the reason for their withdrawal recorded in the final Clinical Pharmacology Study Report (CPSR). All available data from subjects who withdraw will be listed and all available planned data will be included in the summaries according to the populations defined in Section 4.

In the event that the study is prematurely discontinued, all available data will be listed and a review carried out by the study team to assess which statistical analyses are still considered appropriate.

5.6. Derived and Transformed Data

5.6.1. Change from Baseline

The change from baseline will be calculated by subtracting the baseline values from the individual post-baseline values. If either the baseline or post-baseline value is missing, the change from baseline is set to missing as well.

5.6.2. Plasma, Tissues, Fluid Data

Plasma and a variety of compartment tissues and fluid samples are collected during the study, and all will be listed with actual time and calculated visit weeks. Samples with protocol deviation will be reviewed by the team to determine whether these samples will be excluded from the summary tables.

5.6.2.1. Evaluable Concentrations and Parameters

Flags for evaluable concentrations for each type of samples will be created and are defined as samples collected within the specified window without major protocol deviations. Evaluable parameters are calculated based on evaluable concentrations.

Flags will be created for the samples which are collected when the injections are done at gluteal muscle under ultrasound guidance. Concentrations data could be summarized by gluteal muscle flag.

For the purposes of calculating summary statistics and for statistical analysis, only parameters with the exception of tmax will be log_e transformed.

Between subject's coefficient of variation (%CVb) will be calculated according to the following methods:

Untransformed Data : 100 * (SD/Mean)

Transformed Data : $100 * (sqrt(exp(SD_{log}^2)-1))$

where SD_{log} indicates the standard deviation of log-transformed data.

5.6.3. Multiple Measurements at One Timepoint

Where multiple measurements are recorded for a particular time point, the mean of the measurements will be calculated and used in any derivation of summary statistics. However, all available data will be listed.

5.6.4. QTc interval

QTc interval will be corrected by both Bazett's (QTcB) and Fridericia's (QTcF) formula and will be included in all relevant listings.

QTcB interval (msec) = QT interval (msec) / square root (RR interval (msec)/1000)

QTcF interval (msec) = QT interval (msec) / cubic root (RR interval (msec)/1000)

If QTcB is provided by the Electrocardiogram (ECG) machine, then that RR value will be used to calculate the QTcF.

For example, if a vendor provides QTcB but not QTcF, RR will be calculated as:

 $RR = [(QT/QTcB)^{**2}]^{*1000}$, provided at the SDTM level.

5.7. Assessment Windows

Scheduled visits and unscheduled visits for lab, ECG and vital sign data will be assigned to assessment windows by actual study day. For PK, tissues and fluid samples, actual days will be used to calculate the actual visit Week (round-up), and evaluable samples will be summarized by actual visit week. Actual days will be used for the listings, and scheduled windows will be used for the Summary Displays.

Phase	Study Visit and Unscheduled Visit window	Reported on Summary Displays
Screen	30 days prior to Day 1	Screen
Oral Lead-in	Day 1, Day 14, Day 29	Day 1, Day 14, Day 29
Injection phase	Days 1,3,5,8	Days 1,3,5,8
	Week 4 \pm 3 days	Week 4
	Week 8 ±3 days	Week 8
	Week 12 ±3 days	Week 12
	Week 24 ±3 days	Week 24
	Week 36 ±3 days	Week 36
	Week 52 ±3 days	Week 52

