7.5. Pharmacokinetics

Blood samples for plasma pharmacokinetic (PK) analysis of CAB will be collected at the time points indicated in Section 7.1, Time and Events Table. The actual date and time of each blood sample collection will be recorded. With the exception of PK sampling in the first week post-injection which should be performed according to schedule, the timing of PK sample collection may be altered (± 3 days) for scheduling purposes if deemed appropriate by the investigator in consultation with the sponsor.

Blood samples (4 mL each) will be collected into potassium EDTA tubes for plasma CAB analysis, and initial processing will take place as follows:

Immediately after collection, gently invert (DO NOT SHAKE) the evacuated blood collection tube 8-10 times to mix the Potassium Ethylenediaminetetraacetic acid (potassium EDTA) anticoagulant with the whole blood and place the sample(s) on ice.

Within 1 hour of sample collection, separate the plasma by refrigerated (4°C) centrifugation at 1,500 to 2,000 x g for a minimum of 10 minutes.

Immediately after sample processing freeze the plasma storage tubes in the upright position in a non-self-defrosting freezer. Store at -20°C or lower until transfer to bioanalytical facility.

Vaginal, cervical and rectal tissue biopsies and luminal (cervicovaginal and rectal) fluid collections will be done at the time points indicated in Section 7.1. At each female genital tissue sampling time point, up to 3 vaginal and 3 cervical biopsies will be collected via speculum exam per subject. At each rectosigmoid tissue sampling time

point, up to 10 biopsies will be collected at 15 cm from the anal margin via flexible sigmoidoscopy. Details outlining the collection and processing of tissue/ CVF/RF can be found in the SRM.

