5.3. Reporting Conventions

- Statistical data analyses will be performed by, or under the direct auspices of, Clinical Statistics and Programming, GlaxoSmithKline.
- Data will be listed and summarized according to GlaxoSmithKline reporting standards, where applicable. Listings will be sorted by Site, subject, phase, day, and time, noting treatment; summaries will be presented by treatment (for safety and study population) or sex (for PK data), or by Site (demog), day, and time.

- Unless stated otherwise, descriptive summaries will include n, mean, standard deviation (SD), coefficient of variation (%CV), median, minimum, and maximum, geometric mean with associated 95% confidence interval (CI), and the between-subject CV (%CVb) for continuous variables, whereas n and percent will be used as summary statistics for categorical variables.
- Baseline or pre-dose assessment is the last available assessment prior to time of dose administration unless it is specified otherwise. If there are multiple assessments collected on the same scheduled time, the average of these assessments will be used. For tabulated safety summaries, only the scheduled assessments will be included in the summary tables. Unscheduled assessments will be presented in listings.
- Deviations from planned times will be examined for scheduled assessments. PK parameters will be calculated using actual assessment times. Actual assessment times will be used in the individual concentration-time plots. Nominal times will be used for the purposes of summarization and in mean and median plots. Concentration-time data will be listed using actual assessment times.
- Any changes/deviations to the analyses specified in the RAP will be described in the final Clinical Pharmacology Study Report (CPSR).
- Version 9.4 or higher of the SAS system will be used to analyze the CRF data as well as to generate tables, figures, and listings. PK parameters will be calculated using standard non-compartmental methods using Phoenix WinNonLin Version 7 or higher.
- All final displays will be produced according to Clinical Data Interchange Standards Consortium (CDISC) reporting standards based on the final Study Data Tabulation Model (SDTM) and Analysis Data Model (ADaM) datasets.

Data Type	Source	Format of Data	Planned Date of Final File	Responsibility
Safety	Database	SDTM	DBF	Data Management
	SMS2000 /PK HARP	DAT	Prior to SDL	DMPK

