8.3. Deriving and Summarizing Pharmacokinetic Parameters

Pharmacokinetic analyses will be the responsibility of the Clinical Pharmacokinetics Modeling & Simulation department within GlaxoSmithKline.

Plasma and tissue/fluid concentration-time data will be analyzed by non-compartmental methods with Phoenix WinNonlin 7 or higher (New Jersey). Pharmacokinetic parameters will be estimated via noncompartmental analysis using the linear up/log down application of the trapezoidal rule for model 200 (extravascular administration) of the WinNonlin program. Calculations will be based on the actual sampling times recorded during the study. The following CAB PK parameters will be calculated for each matrix if available:

- Cmax, tmax, AUC(0-∞), AUC(0-last), AUC(0-Wk4), AUC(0-Wk8) and AUC(0-Wk12) and t¹/₂ in blood plasma and in CT, and CVF in females and RT and RF in males and females.
- CAB concentrations at Day 3 (C48h), Day 8 (Cd8), Weeks 4, 8, and 12 (CWk4, CWk8, and CWk12) in blood plasma and in CT, CVF in women, and in RT and RF in men and women (as data permit) will be considered as evaluable data if they are collected within 4 hours of schedule time for C48h and Cd8, and collected within ± 3 days of scheduled time for CWk4, CWk8 and CWk12. Actual weeks (rounding to the integer weeks) will be used for CWk24, CWk36 and CWk52.
- 2. VT samples will be considered as evaluable C48h and CWk8 concentration if samples are collected at Day 3 (C48h with 4hrs of window of scheduled collection), and Week 8 (CWk8 with ± 3 days of scheduled visit), in women following a single CAB 600 mg IM dose.
- 3. CAB concentration in VT, CT, CVF, RT, RF and BP on Day 29 will be considered as evaluable data if these samples are collected within 4hr of scheduled window.

- 4. The area under the plasma concentration-time curve from time zero to the last quantifiable concentration (AUC(0-last)) will be determined using the linear trapezoidal rule for increasing concentrations and the logarithmic trapezoidal rule for decreasing concentrations in blood plasma and in CT, and CVF in females and RT and RF in males and females.
- 5. The AUC extrapolated to infinity $(AUC(0-\infty))$ will be calculated, where data permit, as the sum of AUC(0-t) and Ct/ λz , where Ct is the observed plasma concentration obtained from the log-linear regression analysis of the last quantifiable time-point in blood plasma and in CT, and CVF in females and RT and RF in males and females.

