Clinical statistics and programming will extract the Ctau on Day 29, Day 3 (C48h), Day 8 (C8d), Weeks 4, 8, and 12 (CWk4, CWk8, and CWk12) from concentration data to calculate the ratios: CVF:BP, CT:BP, VT:BP, CT:CVF, VT:CVF ratio in women and, RT:BP, RF:BP and RT:RF ratios in males and females at matching time points where data permit during the injection phase.

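### SAP 5.7 rounds PK visit weeks up; read literally, this moves in-window samples out of the visit that SAP 5.3, 8.3 and the rest of 5.7 give them

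*SAP*

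**What the plan says.** Several current statements bear on which visit a PK sample is summarised under, and none is given priority.

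- SAP 5.7, PK clause: "actual days will be used to calculate the actual visit Week (round-up), and evaluable samples will be summarized by actual visit week".
- SAP 5.7, next sentence: "scheduled windows will be used for the Summary Displays". The table below it reports Days 1, 3, 5 and 8, and Weeks 4, 8, 12, 24, 36 and 52 with 3 days either side.
- SAP 5.3: "Nominal times will be used for the purposes of summarization and in mean and median plots".
- SAP 8.3, item 1: a concentration is evaluable if taken within 3 days either side, in "days of scheduled time for CWk4, CWk8 and CWk12".
- SAP 8.3, item 1, later visits: "Actual weeks (rounding to the integer weeks) will be used for CWk24, CWk36 and CWk52". The direction of rounding is not given.
- SAP 5.6.2.1: evaluable concentrations are "defined as samples collected within the specified window without major protocol deviations".
- Protocol 7.5: after the first week "the timing of PK sample collection may be altered" by up to 3 days either way.

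**The concern.** The round-up clause is the only sentence in 5.7 written specifically for PK, tissue and fluid samples, so a programmer could reasonably take it as the governing rule for them. Under a true ceiling, a sample taken 2 days late at Week 8 is evaluable as CWk8 under 8.3 but is summarised as Week 9. No planned display has a Week 9 row, so the sample leaves the Week 8 row and has nowhere to go. The concentrations at Weeks 4, 8 and 12 are primary endpoints, and their descriptive summaries are the primary analysis. A week label also cannot keep the Day 3, Day 5 and Day 8 samples apart, although SAP 8.2 treats them as separate times.

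At stake are the visit label and n in the descriptive concentration and ratio summaries, and which records enter the optional oral-versus-IM model in SAP 8.4, which takes only Day 29 and Weeks 4, 8 and 12.

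**Working it through.** The plan states no figure to reproduce here. The check lists the days in each permitted window and applies each possible rule.

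**Inputs.** The permitted shift is 3 days either side (Protocol 7.5; SAP 5.7 table; SAP 8.3 for Weeks 4, 8 and 12). Injection is on Day 1, 48 h is Day 3 and 168 h is Day 8 (SAP 8.2), so study day = elapsed days + 1. I assume that Week w falls 7w elapsed days after injection, which fits 168 h being one week. The PK clause does not say whether its days are elapsed days or study days, so both are shown.

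**Week 4.** With d the elapsed days:

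| d | 25 | 26 | 27 | 28 | 29 | 30 | 31 | Moved |
|---|---|---|---|---|---|---|---|---|
| Round up d/7 | 4 | 4 | 4 | 4 | 5 | 5 | 5 | 3 of 7 |
| Round up (d+1)/7 | 4 | 4 | 4 | 5 | 5 | 5 | 5 | 4 of 7 |
| Nearest integer to d/7 | 4 | 4 | 4 | 4 | 4 | 4 | 4 | 0 of 7 |
| Nearest integer to (d+1)/7 | 4 | 4 | 4 | 4 | 4 | 4 | 5 | 1 of 7 |
| Scheduled window | 4 | 4 | 4 | 4 | 4 | 4 | 4 | 0 of 7 |

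The counts repeat at Weeks 8, 12, 24, 36 and 52, because each scheduled day is a multiple of 7. On elapsed days the ceiling sends days 29–31 to Week 5, 57–59 to Week 9 and 85–87 to Week 13. On study days even the on-time Week 4 visit moves: 29/7 = 4.14, which rounds up to 5. Over Weeks 4, 8 and 12 together, the rows of the table give 9, 12, 0, 3 and 0 of 21 permitted days moved.

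**Agreement of nearest-integer rounding with the 5.7 table.** On elapsed days the label first changes at 4 days off schedule: 24/7 = 3.43 gives Week 3, and 32/7 = 4.57 gives Week 5. The rule therefore matches a window of 3 days either side.

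**First week.** Elapsed days 2, 4 and 7 round up to Week 1, 1 and 1; to the nearest integer they give Week 0, 1 and 1. Neither rule separates Days 3, 5 and 8.

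**Effect on a row.** The plan aims for 8 evaluable men and 8 evaluable women. One late visit takes a sex-by-visit row from n = 8 to n = 7. The documents give no distribution of actual visit days. If the share of visits 1 to 3 days late were 0, 10%, 20% or 3/7 (uniform over the window), the expected loss per row of 8 would be 0, 0.8, 1.6 or 8 × 3/7 = 3.4. These shares are assumptions for illustration only.

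**The case against.** The strongest reply is that harm requires ignoring the rest of 5.7. The next sentence gives scheduled windows to the Summary Displays, and the table has no Week 5, 9 or 13 to receive a moved sample. SAP 5.3 uses nominal times. SAP 8.3 defines the named endpoints by window and extracts "Weeks 4, 8, and 12 (CWk4, CWk8, and CWk12) from concentration data to calculate the ratios". Its rounding for the later visits does not say up, so nearest-integer rounding may be what was meant throughout. A ceiling would clash with the display list as soon as it was programmed.

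Most of this stands. It makes a harmless outcome likely and lowers the weight of the point. It does not remove the need to edit. If the scheduled windows govern, the clause is wrong and should go. If nearest-integer rounding was meant, the text says something else, the day origin is still missing (1 of 7 days moves on study days), and the first-week labels still fail. SAP 5.6.2 also plans to list samples with calculated visit weeks, so a week variable will be derived.

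From 3 of 7 days a reader might infer that about 43% of the Week 4, 8 and 12 results would be misfiled, or that the primary results would be wrong. The documents support neither. The ratio counts calendar days in a window, not samples, and the share of late samples is unknown. The endpoints are defined by window in 8.3, and the listings keep actual times.

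**Conclusion.** The contradiction is in the current text, and the literal rule gives the wrong visit for samples the plan itself calls evaluable: 3 of 7 permitted days per week visit on elapsed days, or 4 of 7 on study days. Under the scheduled windows, or with nearest-integer rounding of elapsed days, no in-window sample moves at Weeks 4 to 52.

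The consequence is limited to visit labels and n in the descriptive concentration and ratio summaries, and to records entering the optional exploratory model. AUC, Cmax, tmax and t½ are computed from actual times and do not change. No hypothesis is tested. The number of samples affected cannot be derived and may be zero. Severity: minor. The counts rest on whole-day arithmetic and on Week w falling 7w days after injection.

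**What to change.** In SAP 5.7, delete the round-up parenthesis and the clause after it that summarises evaluable samples by actual visit week. Replace them with wording such as:

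*Days are elapsed days from injection. Evaluable PK, tissue and fluid samples are summarised under the scheduled visit (Days 1, 3, 5 and 8; Weeks 4 to 52), using the windows in the table below and the evaluability windows in Section 8.3.*

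This agrees with 5.3 for every in-window sample, so 5.3 needs no change.

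Keep the 5.7 windows in force for PK. Confining them to laboratory, ECG and vital-sign data would leave no placement rule for plasma samples taken at the Withdrawal visit (Protocol 7.1.2) or after a liver stopping event (Protocol Appendix 2).

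State that Tables 3.9 and 3.11, the visit-level ratio tables with no evaluable-flag split, use evaluable samples only. State also that out-of-window samples appear in the listings and in the displays split by that flag.

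In SAP 8.3, specify that rounding for CWk24, CWk36 and CWk52 means elapsed days divided by 7, to the nearest integer. This matches the windows already in the 5.7 table and adds no new evaluability rule for those visits.

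The cost is a few sentences in 5.7 and 8.3 and a note on two tables. The 5.7 table and the data collection do not change.

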5.8. Values of Potential Clinical Importance

ECG Values of Potential Clinical Importance (Healthy Volunteers)

ECG Parameter	Potential Clinical Importance Range (PCI)	Unit
Absolute QTc interval	>450	msec
Increase from baseline QTc	>60	msec
PR interval	<110 and >220	msec
QRS interval	<75 and >110	msec

Vital Sign Values of Potential Clinical Importance (Healthy Volunteers)

Parameter	Potential Clinical Importance Range (PCI)	Unit
Systolic Blood Pressure	< 85 and > 160	mmHg
Diastolic Blood Pressure	< 45 and > 100	mmHg
Heart Rate	< 40 and > 110	bpm

6. STUDY POPULATION

Study population data will be summarised by, or under the direct auspices of, Clinical Statistics, GlaxoSmithKline.

6.1. Overview of Planned Study Population Analyses

The study population analyses will be based on the screened and safety population, unless otherwise specified.

Study population analyses including analyses of subject's disposition, protocol deviations, demographic and baseline characteristics, prior and concomitant medications, and exposure and treatment compliance will be based on GSK Core Data Standards if applicable. Details of the planned displays are presented in Section 11.1.1 and Section 11.1.4 of the RAP.

6.2. Subject Disposition

A summary table will be generated to provide the count of subjects included in each analysis population for the study (see Section 4 for definition of analysis populations) and this table will be displayed by treatment and overall.

The End of Study Record will be listed and summarized by Site and overall. The listing will include whether subjects prematurely withdrew from the study, the reason for premature discontinuation, along with the start and end date of investigational product (IP) dosing and the date of completion or premature discontinuation from the study.

6.3. Demographic and Baseline Characteristics

Demographic data includes date of birth, gender, race, and ethnicity. Demographic data will be summarized by Site and Overall, and listed for the Safety Population. Race will be summarized by Site and Overall, and listed separately from the other demographic characteristics.

Baseline characteristics (Height, weight, BMI, etc.) will be listed by subject and summarized by Site and Overall according to data display specifications given in Section 11.1.2 and Section 11.1.4.

6.4. Concomitant Medications

Concurrent medication verbatim text will be coded and classified by the Anatomical Therapeutic Chemical Classification level 1 (ATC Level 1) code and the preferred term using the GSK coding system, GSK DRUG. Subjects who take concurrent medications during the study will be summarized and listed according to data display specifications given in Section 11.1 of this RAP. Coding of concurrent medications will be the responsibility of the GSK coding group.

Information on whether or not the subject consented to having a pharmacogenetic sample drawn will be listed.

6.5. Treatment Compliance and Protocol Deviations

Information for each subject who did not receive the correct dose, the reason for not receiving the correct dose, and any other protocol deviations will be summarized by the important flag and by Site and listed by Site and subject. Subjects who did not satisfy all inclusion and exclusion criteria and corresponding criteria that were violated will be listed.

7. SAFETY ANALYSES

Safety data will be summarised descriptively and listed by according to GSK's Integrated Data Standards Library (IDSL) standards, or under the direct auspices of, Clinical Statistics, GlaxoSmithKline

No formal statistical analysis of the safety data will be conducted.

The precise format and content of Safety figures, tables and listings are shown in Section 11.1.2 and Section 11.1.4 of the RAP.

The tables will use the "Safety" population unless otherwise specified.

7.1. Extent of Exposure

A by-subject summary of treatments administered in each phase will be generated, with dose, number of doses and dosing start date and dosing end date. A by-subject listing of

data on subject exposure will be generated including dose date and time, unit, formulation, route, frequency and location.

7.2. Adverse Events

Adverse event verbatim text will be coded and classified by system organ class (body system) and preferred term using a standardized GSK coding system: Medical Dictionary for Regulatory Activities (MedDRA, v22 or higher). Treatment emergent AEs data and drug-related AEs for lead-in phase and for LA dosing phase will be summarized by Site and treatment and overall. The relationship of AE system organ class, preferred term, and verbatim text will be listed. All AEs will be listed by Site, subject and treatment. Serious adverse events (SAEs) will be listed. A listing of grade 3 or 4 non-ISR AEs will be provided if any grade 3 or 4 AE occur.

Injection site reaction (ISR) symptoms, size, severity grade and duration for the LA dosing phase will be summarized overall and will be listed by Site and subject.

For subjects who have an ISR that is serious, Grade 2 if persistent beyond 2 weeks, any Grade 3 or if any ISR persistent beyond 30 days and others if the Investigator or Medical Monitor feels it is medically necessary, a listing will be provided in table listing. All ISR data including treatment received and medical intervention as well as reaction outcome will be listed by subject. Plots of top 3 injection site reaction duration will be provided.

